This is a retrospective controlled survey-study to assess the safety of treating migraine with Nerivio during pregnancy and 3 months postpartum. We will compare migraine and pregnancy related health and baby health between women with migraine who treated migraine attacks during pregnancy with Nerivio (Nerivio group), to women with migraine who did not treat migraine attacks during pregnancy with Nerivio (control group). Nerivio group participants will be recruited from Theranica's user base. Control group participants will be recruited by health care providers, including headache specialists and OBGYNs (study co-investigators). The study is fully electronic, including an e-eligibility questionnaire, an e-ICF, and an e-survey. Participants will be compensated for their time.

Goal

Assess the safety of treating migraine with Nerivio during pregnancy and 3 months postpartum.

Study Design

Retrospective controlled survey-study.

Study group: Postpartum patients with migraine who used Nerivio at least 3 times during their "study pregnancy"

Control group: Postpartum patients with migraine who did not use Nerivio during their "study pregnancy"

Eligibility

Inclusion criteria:

- 1. Diagnosed with migraine
- 2. History of migraine pre-pregnancy with an average of at least 4 migraine days per month, in the six months prior to the last pregnancy
- History of pregnancy with last menstrual period (LMP) between November 1st, 2019 –
 March 31st, 2021. Pregnancy within this time window is the pregnancy of study, termed
 "study pregnancy"
- 4. Between 18 and 42 years of age at first day of the last menstrual period (LMP) of "study pregnancy"
- 5. History of at least 4 migraine attacks during "study pregnancy"
- 6. In the study group: usage of Nerivio for at least 3 treatments (≥30 minutes/treatment) during "study pregnancy"
- 7. In the control group: No history of using Nerivio, ever

TCH-011 Clinical Study Protocol

Doc ID: TECXXXX

Revision #: 1.0

Page: 5 of 25

Exclusion criteria:

- 1. History of preterm birth (gestational age at deliver<37 weeks) in previous pregnancies prior to the "study pregnancy"
- 2. History of congenital malformations or birth defects in previous pregnancies prior to the "study pregnancy"
- 3. Severe other diseases which started before the "study pregnancy" and lasted into the "study pregnancy" period, including congenital heart disease, arrhythmia, history of myocardial infarction (MI), history of stroke, or active cancer
- 4. Serious physical injury that occurred during the "study pregnancy": severe car collision injury, serious injury at home/work, etc. Multiple gestation (i.e., pregnancy with more than one baby at a time, such as pregnancy with twins, triplets, and quadruplets) in the "study pregnancy"

Study Design and Recruitment

Study group: Study group participants will be recruited from Nerivio's user base. An invitation message will be sent via in-app notification and/or email to all Nerivio users who are (1) female, AND (2) between 18 and 42 years of age as of November 1st, 2019 - March 31st, 2021. Users who meet these criteria will be invited to fill in a screening and eligibility questionnaire. If they meet the eligibility criteria, they will be offered the opportunity to participate in the study. Participants will complete and sign an electronic informed consent form. Following consent, participants will be asked to complete the questionnaire. Once complete, participants will be compensated for their time.

Control group: Control group participants will be referred to the study by site co-investigators, who are US licensed healthcare providers seeing women with headache disorders and/or women during their pre-pregnancy and/or pregnancy period. Patients interested in participating will be directed to the same screening and eligibility questionnaire and will follow the same study design.

Endpoints

Endpoints focus on the health of the mother and the baby, during pregnancy and three months postpartum.

Primary endpoint:

Demonstrate that the study group is not different than the control group in regard to gestational age at delivery (measured in pregnancy weeks).

QMS document

TCH-011 Clinical Study Protocol

Doc ID: TECXXXX

Revision #: 1.0

Page: 6 of 25

Secondary endpoints:

Demonstrate that the study group is not different from the control group in:

- 1. Baby's birth weight (average birth weight)
- 2. Miscarriage rate (% of miscarriage cases)
- 3. Preterm birth rate (% cases of preterm pregnancies, as measured in % of pregnancy weeks less than 37)
- 4. Birth deficits rate (% of birth deficits)
- 5. Still births rate (% of still births)
- 6. Meeting developmental milestones following 3 months postnatal (% of babies)
- 7. Visits to the emergency room or urgent care due to pregnancy and/or migraine symptoms during pregnancy and 3 months postpartum period (# of events)

Exploratory endpoints: Difference between the study group and the control group in:

- 1. Overall subjective **feeling of safety** using acute migraine treatments during pregnancy (in subjects who used such treatments).
- 2. Overall subjective **satisfaction** with the acute migraine therapies used during the pregnancy (in subjects who used such treatments).
- 3. APGAR score at 5 minutes.

Data analysis

Statistical Hypothesis

The goal of the proposed study is to test the null hypothesis that treating with Nerivio during pregnancy does not impose a safety risk relative to standard care migraine treatment for pregnant women. In other words, the hypothesis is that the means of the two populations are equal. Thus, in this study, the following hypotheses will be tested:

• Null hypothesis: H0: GAt = GAc

• Alternate hypothesis: H1: GAt ≠ GAc

Where GAt and GAc are the average Gestational Age in the study group and control group, respectively. If the null hypothesis is not rejected, the study will be deemed successful. The criterion for significance has been set at 0.05. The test is 2-tailed.

TCH-011 Clinical Study Protocol

Doc ID: TECXXXX

Revision #: 1.0

Page: 7 of 25

Planned Sample Size

Based on USA data from 2020 [Osterman M, et al. Births: Final Data for 2020. Natl Vital Stat Rep. 2021] we assume mean gestational age (GA) of 38.4 with standard deviation of 2.7 (range 26-42).

With the proposed sample size of 114 for each group, the study will have power of 80% to yield a statistically significant result. This computation assumes that the mean difference is less than 1.0 week, and the common within-group standard deviation is 2.7. This effect was selected as the smallest effect that would be important to detect.

Precision for estimating the effect size: We further estimate the mean difference between the two populations. On average, a study of this design would enable us to report the mean difference with a precision (95% confidence level) of plus/minus 0.70 weeks.

Given this statistical requirement up to 400 participants will be recruited per group.

Statistical Analysis Plan

Data will be collected from all patients recruited to the study. Data analysis will not include patients who are:

- Obese (BMI>=40) at the beginning of the study pregnancy
- Did not have their last menstrual period (LMP) between November 1st, 2019 March 31st, 2021
- In the study group, did not use Nerivio for at least 3 treatments (≥30 minutes/treatment) during the "study pregnancy"
- In the control group, did use Nerivio before, during, or in the 3 months following the "study pregnancy"

TCH-011 Clinical Study Protocol

Doc ID: TECXXXX

Revision #: 1.0

Page: 8 of 25

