- 22. If you had a miscarriage, what was its cause?
 - I did not experience a miscarriage
 - Abnormal fetal development

QMS document

TCH-011 Clinical Study Protocol

Doc ID: TECXXXX

Revision #: 1.0 Page: 18 of 25

- Abnormal placenta (such as abruption)
- Blood disorders such as thrombophilias
- Cervical insufficiency
- Chromosomal abnormalities
- Maternal anatomic abnormalities such as uterine fibroids, polyps or adhesions in uterus
- Physical trauma
- Unknown cause
- Other

23. Delivery circumstances (Check all that applies)

- Spontaneous labor
- Induction of labor
- Past due date
- Decreased fetal movement
- Cardiac arrhythmia in fetus
- Pregnancy induced hypertension such as gestational hypertension or pre-eclampsia
- HELLP syndrome
- Premature rupture of membranes
- Other complications or medical concerns

Check all that apply

24. What was the mode of delivery?

- Repeat Cesarean Delivery
- Primary Cesarean delivery
- Spontaneous vaginal delivery

25. During your "study pregnancy", did you do any of the following (select all that apply)

Smoking

QMS document

TCH-011 Clinical Study Protocol

Doc ID: TECXXXX Revision #: 1.0

Page: 19 of 25

•	Excessively consuming alcohol (more than 1 glass of wine/day or any other
	equivalent)

- Using recreational drugs

Using medical marijuana

Check all that apply

26. Was the baby discharged from the hospital at the same time with yo	u?
--	----

- Yes
- No
- 27. Did you use Nerivio to treat your migraine attacks during your "study pregnancy"?
 - Yes
 - No
- 28. During your "study pregnancy", did you use Nerivio for migraine treatment at least 3 times?
 - Yes
 - No

Part 3 – Migraine during the study pregnancy

The following questions refer to your latest, completed, pregnancy referred to as the "study pregnancy" (if you are currently pregnant, please do not refer to this pregnancy when answering the questionnaire).

- 29. How many migraine days per month (on average) did you have during the FIRST trimester of your "study pregnancy"?
 - Less than 4 days per month
 - 4-8 days per a month
 - 9-14 days per month
 - 15 days or more per month

Multiple choice

30. How often did you use ACUTE treatments for migraine during the FIRST trimester of your "study pregnancy"?

QMS document

TCH-011 Clinical Study Protocol

Doc ID: TECXXXX

Revision #: 1.0

Page: 20 of 25

- Less than 4 times per month
- 4-8 times per a month
- 9-14 times per month
- 15 times or more per month

Multiple choice

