TCH-011 Clinical Study Protocol

Doc ID: TECXXXX

Revision #: 1.0

Page: 22 of 25

- Other devices (e.g., gammaCore[™], Cefaly[®], Relivion[®])
- Zofran® (Ondansetron), Reglan® (Metoclopramide), Compazine® (Prochlorperazine),
 Phenergan® (Promethazine), or any other medication for nausea/vomiting
- Other medications
- None

Check all that applies

36. Rate your overall satisfaction with your acute migraine treatment during your "study pregnancy", when 1 = Highly dissatisfied, 10 = Highly satisfied

Drop Down menu, with options 1-to-10 AND Not relevant (I did not use acute migraine treatment during my pregnancy)

37. Please mark all types of PREVENTIVE treatments (either pharmaceutical drugs and/or devices) you used for migraine during the "study pregnancy". Please include any treatment, even if used only once.

For each treatment type used, please indicate if you felt safe using it during the pregnancy by choosing the matching option of the dropdown menu.

- Amitriptyline, or any other generic tricyclic antidepressants
- Inderal[®] (Propranolol)
- Topiramate® (Topamax)
- Other generic oral preventive medication
- Nortriptyline (Pamelor), or any othernon-generic tricyclic antidepressants
- Botox® injection for migraine prevention (Botulinum toxin)Aimovig® (Erenumab),
 Ajovy® (Fremanezumab), Emgality® (galcanezumab-gnlm), Vyepti® (eptinezumabjjmr), that is any CGRP monoclonal antibodies (CGRP mAbs)
- Nurtec® ODT (Rimegepant)
- Devices (e.g., gammaCore, Cefaly)
- Other
- Did not use any preventive treatment
- 38. Rate your overall satisfaction with your PREVENTIVE migraine treatment during your "study pregnancy", when 1 = Highly dissatisfied, 10 = Highly satisfied

Drop Down menu, with options 1-to-10 AND Not relevant (I did not use preventive migraine treatment during my pregnancy)

TCH-011 Clinical Study Protocol

Doc ID: TECXXXX
Revision #: 1.0

Page: 23 of 25

- 39. Were you admitted to the emergency room (ER) or hospital for management/evaluation of headache during your "study pregnancy"?
 - Yes
 - No

Part 4 - Migraine postpartum

- 40. How many migraine days per month (on average) did you have in the 3 months postpartum after your "study pregnancy"?
 - Less than 4 days per month
 - 4-8 days per a month
 - 9-14 days per month
 - 15 days or more per month
- 41. Did you breast-feed during the first 3 months postpartum following your "study pregnancy"?
 - Yes
 - No

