Part 5 – Baby's health

- 42. For your "study pregnancy", what is your baby's sex at birth?
 - Male
 - Female
- 43. What was the baby's birth weight (lbs)?

Choose on a drop-down menu, including the following answers:

- Less than 1.5 kg / 3.4 pounds
- Between 1.5 and 2.49 kg / between 3 pounds 4 ounces and 5 pounds 8 ounces
- Weights with jumps of 100 gram up to 4 kg and the equivalent in pounds (2.5, 2.6, 2.7, 4)
- More than 4 kg / 8 pounds and 13 ounces

QMS document

TCH-011 Clinical Study Protocol

Doc ID: TECXXXX
Revision #: 1.0

Page: 24 of 25

44.	Was	the	baby	diagnosed	with	any	birth	defects?
-----	-----	-----	------	-----------	------	-----	-------	----------

- No
- Yes
- 45. Were there any complications with the baby after delivery?
 - No
 - Yes

If Yes, what type of complication?

- Neonatal jaundice,
- Newborn required admission to the neonatal intensive care unit
- Respiratory distress syndrome
- Infection such as sepsis
- Failure to thrive
- Low birth weight
- Other
- 46. Did your baby meet routine developmental milestones at 3 months? of life (such as smiling, gurgle, visually tracking objects, and rolling over within the first 3 months)
 - No
 - Yes
- 47. What was your baby's APGAR scores at 1 minute after birth?

We know it might be difficult to remember this score. Please check your discharge notes to find the 1 minute APGAR score, although not all notes include this information:

- Choose 1-10
- Don't know / Can't find the 5 min APGAR score

Use a dropdown menu, and add the option can't find

48. What was your baby's APGAR scores 5 minutes after birth? We know it might be difficult to remember this score. Please check your discharge notes to find the 5 minutes APGAR score, although not all notes include this information:

QMS document

TCH-011 Clinical Study Protocol

Doc ID: TECXXXX

Revision #: 1.0

Page: 25 of 25

- Choose 1-10
- Don't know / Can't find the 5 min APGAR score

Use a dropdown menu, and add the option can't find

- 49. Does the baby have any additional APGAR scores at 10, 15 or 20 minutes?
 - Yes
 - No
 - Don't know

If Yes, go to the next page, and ask for APGAR scores at 3 additional time points. Otherwise (answer: No or Don't know), go directly to the last page.

Page break

- 50. What was your baby's APGAR scores 10 minutes after birth? We know it might be difficult to remember this score. Please check your discharge notes to find the 5 minutes APGAR score:
 - Choose 1-10

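### Maternal safety rests on one endpoint that the survey cannot supply; the maternal and neonatal complications it collects have no specified analysis, and device adverse effects are not asked about

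*Combined protocol and SAP*

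**What the plan says.** The study sets out to "assess the safety of treating migraine with Nerivio during pregnancy and 3 months postpartum", and the Endpoints section adds: "Endpoints focus on the health of the mother and the baby, during pregnancy and three months postpartum". The opening summary promises a comparison in general terms: "We will compare migraine and pregnancy related health and baby health between women with migraine who treated migraine attacks during pregnancy with Nerivio" and those who did not.

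The primary endpoint is: "Demonstrate that the study group is not different than the control group in regard to gestational age at delivery (measured in pregnancy weeks"). Secondary endpoints 1 to 6 are birth weight, miscarriage, preterm birth, birth defects, stillbirth and developmental milestones at 3 months. Secondary endpoint 7 is: "Visits to the emergency room or urgent care due to pregnancy and/or migraine symptoms during pregnancy and 3 months postpartum period (# of events"). The exploratory endpoints are feeling of safety, satisfaction with acute treatment, and the 5-minute APGAR score.

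In Appendix 2, item 39 asks "Were you admitted to the emergency room (ER) or hospital for management/evaluation of headache during your" study pregnancy, with yes or no as the answers. Item 23, on delivery circumstances, includes the option "Pregnancy induced hypertension such as gestational hypertension or pre-eclampsia" and a separate one for HELLP. Item 45, on complications in the baby, includes "Newborn required admission to the neonatal intensive care unit", respiratory distress syndrome and infection.

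Under Statistical Hypothesis, the study succeeds if equality of mean gestational age is not rejected. The Statistical Analysis Plan section lists only which patients are left out of the analysis.

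**The concern.** The stated scope is the safety of mother and baby, but the endpoint list hardly reaches the mother. A woman's own illness enters only through emergency visits, and the survey item behind that endpoint does not measure what the endpoint defines. Complications of direct safety interest are asked about without any plan for comparing them, so whether and how they are reported would be decided after the data are seen.

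Two losses could not be repaired once the survey closes. One is hypertensive disease that was not part of the delivery event. The other is any adverse effect that a user attributes to the device. The study could then be declared successful on gestational age with these outcomes unexamined or never recorded.

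**Working it through.** **1. The plan's own figure.** Inputs from Planned Sample Size and Statistical Hypothesis: difference 1.0 week, SD 2.7, two-sided 0.05, power 80%.

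- n per group = 2 × (1.960 + 0.8416)² × 2.7² / 1.0² = 114.4, rounded up to 115, against 114 stated. Power at 114 is 79.8%.
- 95% half-width at 114 = 1.96 × 2.7 × √(2/114) = 0.70 weeks, as stated.

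These figures reproduce and are not in dispute. They concern gestational age only.

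**2. What the endpoints cover.** There are 1 + 7 + 3 = 11 endpoints.

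- Pregnancy outcome or baby: 8 (gestational age, birth weight, miscarriage, preterm birth, birth defects, stillbirth, milestones, APGAR).
- The mother's subjective ratings: 2 (feeling of safety, satisfaction).
- A health event in the mother herself: 1 (endpoint 7).

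**3. Endpoint 7 against its only source, item 39.**

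| Element | Endpoint 7 | Item 39 |
|---|---|---|
| Measure | number of events | yes/no |
| Setting | emergency room or urgent care | emergency room or hospital admission |
| Reason | pregnancy and/or migraine symptoms | headache |
| Period | pregnancy and 3 months postpartum | pregnancy |

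Every row differs. The postpartum part of the survey (items 40 and 41) asks only about migraine days and breast-feeding, so it cannot fill the gap.

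**4. Collected without a specified analysis, or not collected.**

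- Item 23 (gestational hypertension or pre-eclampsia, HELLP) and item 45 (NICU admission, respiratory distress, infection) feed no endpoint and no stated analysis.
- Item 23 asks about the circumstances of delivery. A woman whose hypertensive disease was not tied to delivery, or arose after it, has no clear reason to tick the option.
- Items 14, 27 and 28 ask whether and how often Nerivio was used. Item 35 asks whether the user felt safe with each treatment. None of the 52 items asks about an adverse effect of the device.

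**5. What added comparisons could show.** The documents give no complication rates, so those below are assumptions. With the same rate p in both groups, the 95% half-width of the risk difference is 1.96 × √(2p(1 − p)/n).

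| Assumed rate | Expected events per group, n = 114 / 400 | Half-width in points, n = 114 / 400 |
|---|---|---|
| 3% | 3.4 / 12 | 4.4 / 2.4 |
| 5% | 5.7 / 20 | 5.7 / 3.0 |
| 10% | 11.4 / 40 | 7.8 / 4.2 |

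Power for 10% against 20% (arcsine approximation): h = 2·asin(√0.20) − 2·asin(√0.10) = 0.9273 − 0.6435 = 0.2838, and power = Φ(h√(n/2) − 1.96).

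- n = 114: Φ(2.143 − 1.96) = 57%.
- n = 400: Φ(4.013 − 1.96) = 98%.

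For 10% against 15%, the same formula gives about 21% and 57%.

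HELLP alone is a different matter. At an assumed 0.1% to 0.5%, the chance of no case in a group, (1 − p)^n, is 89% to 56% at n = 114 and 67% to 13% at n = 400. This is why it belongs in a composite.

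**The case against.** Which collected variables become named endpoints is a design choice, and items 23 and 45 could legitimately be descriptive. Miscarriage, stillbirth and preterm birth are arguably maternal as well as fetal outcomes, and the 5-minute APGAR score gives some view of neonatal condition. An adverse-effect question has no control counterpart and depends on long recall. These points have weight. They limit what can be said about coverage and mean that device effects can only be described. They do not make endpoint 7 derivable, and they do not recover hypertensive disease or device effects that the survey fails to ask about.

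A reader might infer two stronger things that the documents do not support.

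- That these complications will never be compared. The opening summary promises a general comparison of pregnancy-related and baby health. What is absent is any named outcome or method.
- That the omitted outcomes are the ones with enough events to be informative. This rests on assumed rates. Preterm birth is already an endpoint and at the same assumed 10% has the same power, and gestational age is continuous. At 114 per group, 57% power for a doubling is not strong.

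**Conclusion.** The point stands as a gap in coverage and specification. One of eleven endpoints records a maternal health event, and item 39 differs from it in measure, setting, reason and period. The complications in items 23 and 45 have no specified analysis, hypertensive disease not tied to delivery may be missed, and device adverse effects are not recorded. This rests on the text alone. Counting miscarriage, stillbirth and preterm birth as partly maternal would change the tally but not the finding that maternal illness is otherwise unmeasured.

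The primary analysis and its sample size are unaffected. The precision figures depend on assumed rates of 3-10% and support estimation with intervals, not a conclusion of no difference.

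**What to change.** (a) Name two secondary safety endpoints: a composite of gestational hypertension, pre-eclampsia or HELLP; and, among live births (item 21), a composite of NICU admission, respiratory distress or neonatal infection. Report each as a risk difference with its 95% CI, not as a claim of no difference.

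(b) Move the hypertension and HELLP options out of item 23 into a stand-alone item asking about diagnosis at any time in the study pregnancy or the 3 months postpartum.

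(c) After item 28, add a short branch for Nerivio users: any adverse effect from a treatment in the study pregnancy, what it was, and its outcome. Report it descriptively for the Nerivio group only.

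(d) Align item 39 with endpoint 7: emergency room or urgent care, pregnancy or migraine symptoms, number of visits, pregnancy and 3 months postpartum.

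(e) State that success on gestational age alone does not establish maternal or neonatal safety. Adding endpoints leaves that success rule in place, so this needs saying outright.

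Cost: two more comparisons and a few minutes of survey time, with no extra participants. The neonatal composite uses data already collected, but the hypertensive composite rests on a new item. The adverse-effect data will be limited by recall and will have no control counterpart. The screening message that gives the number of questions would need updating.

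### The secondary safety endpoints aim to demonstrate no difference but have no margin, test, confidence interval or power; for stillbirth at 114 per group a non-significant result is near certain even if the risk triples

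*Combined protocol and SAP*

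**What the plan says.** The list of secondary endpoints (Endpoints, Secondary endpoints) opens with "Demonstrate that the study group is not different from the control group in" and names seven outcomes. Among them are "Miscarriage rate (% of miscarriage cases)", "Birth deficits rate (% of birth deficits)" and "Still births rate (% of still births)". The others are mean birth weight, preterm birth, developmental milestones at three months, and emergency or urgent-care visits.

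The Statistical Hypothesis section states one pair of hypotheses, for gestational age only: "Null hypothesis: H0: GAt = GAc" against inequality. It adds "The criterion for significance has been set at 0.05" and "The test is 2-tailed", and sets the success rule: "If the null hypothesis is not rejected, the study will be deemed successful".

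The Planned Sample Size section justifies 114 per group on gestational age and allows recruitment of up to 400 per group. The Statistical Analysis Plan section lists only which participants are left out of the analysis. No section gives any secondary endpoint a margin, an expected rate, a test, an interval or a power.

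**The concern.** To show that two groups do not differ, one needs a stated difference that would be too large to accept and an interval that excludes it. A test of equality that fails to reject does neither, and the less informative the data, the more easily it fails to reject. For a rare binary outcome in groups of this size there may be so few events that the test can hardly reject at all.

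Stillbirth and birth defects are among the gravest outcomes in a study whose purpose is to assess safety in pregnancy. If the analyst, having no other criterion, applies the gestational-age rule to them, the report could say that no difference was demonstrated on data that cannot exclude a several-fold increase.

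**Working it through.** **1. The plan's own figure.** Inputs from Planned Sample Size: difference 1.0 week, SD 2.7, two-sided 0.05, 80% power.

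n per group = 2 × [SD × (1.960 + 0.842) / difference]² = 2 × (2.7 × 2.802)² = 114.4.

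At 114 per group the power is 79.8%, and the 95% half-width is 1.96 × 2.7 × √(2/114) = 0.70 week. Both agree with the plan. This supports gestational age only and says nothing about the binary endpoints.

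**2. What a non-significant stillbirth result can look like.** With no events in one group and k in the other, the two-sided Fisher p-value for equal groups of n is 2 × C(n,k) / C(2n,k). At n = 114:
- k = 5: 2 × C(114,5) / C(228,5) = 0.060, not significant.
- k = 6: 2 × C(114,6) / C(228,6) = 0.029, significant.

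So 5 events against 0 (5/114 = 4.4% against 0%) would still count as non-rejection.

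**3. Chance of missing a real increase.** The documents give no baseline risks and name no test. The control risks below are assumptions, and the test is taken as Fisher's exact, two-sided 0.05. For control risk p and true risk ratio R:

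P(non-significant) = 1 − Σ Bin(x; n, p) × Bin(y; n, Rp), summed over all pairs (x, y) with Fisher p below 0.05.

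| Outcome and assumed control risk | True ratio | Missed, n = 114 | Missed, n = 400 |
|---|---|---|---|
| Stillbirth 0.5% | 3 | 99.6% | 83% |
| Stillbirth 0.6% | 2 | 99.9% | 94% |
| Stillbirth 0.6% | 3 | 99.1% | 77% |
| Stillbirth 1% | 2 | 99.0% | 87% |
| Stillbirth 1% | 3 | 95.0% | 56% |
| Birth defects 3% | 2 | 89% | 52% |
| Birth defects 3% | 3 | 61% | 6% |
| Miscarriage 10% | 2 | 50% | 2.5% |
| Miscarriage 10% | 3 | 3.7% | below 0.1% |

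Over a wider assumed range for birth defects, 2% to 5%, a doubling is missed 78% to 94% of the time at 114 and 26% to 68% at 400. A tripling is missed 35% to 79% and 0.3% to 20%.

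An uncorrected chi-square test is somewhat less conservative but gives the same pattern. For stillbirth at 0.6% and n = 114, its power is 2.6% for a doubling and 7.8% for a tripling.

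**4. What zero events would show.** With no events among n, the upper two-sided 95% limit is 1 − 0.025^(1/n). This is 3.2% at n = 114 and 0.9% at n = 400. A group of 114 without a single stillbirth is therefore still compatible with a true risk of 3%, three times an assumed 1%.

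**The case against.** Four objections carry weight.

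- **The success rule is written for gestational age only.** This is correct. Nothing in the documents says that non-rejection on a secondary endpoint counts as success or will be reported as safety. Carrying it over is an inference from the shared wording and the absence of any other criterion. If it does not carry over, the secondary endpoints have a stated aim and no way of judging whether it was met, and the same repair is needed.
- **Up to 400 per group may be recruited, and that matters.** It does: at 400, a tripling of birth defects from an assumed 3% is detected 94% of the time. But 400 is a ceiling, while the stated requirement is 114, and stillbirth remains poorly covered even at 400.
- **Miscarriage is not necessarily rare.** This stands. A reader might infer that non-significance is almost guaranteed for miscarriage, birth defects and stillbirth alike, even after a doubling or tripling. The documents do not support that. At an assumed 10% miscarriage risk, a tripling is detected about 96% of the time at 114, and a doubling about 97% of the time at 400. The stronger reading would need a low miscarriage rate in this sample, such as 2% to 5%, and the plan gives no rate.
- **All baseline risks here are assumed.** True, and the percentages move with them. The logical gap does not: non-rejection fails to demonstrate no difference at any baseline rate.

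**Conclusion.** The concern holds in a limited form. The plan sets out to demonstrate no difference on seven secondary endpoints without a margin, test, interval or power for any of them, and its only criterion would, if carried over, treat non-significance as the demonstration.

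The size depends on the outcome and on the assumed control risk:
- **Stillbirth (0.5% to 1%).** Non-significance is near certain at 114 per group even after a tripling. It is still more likely than not at 400.
- **Birth defects (3%).** Missing a doubling is likely at 114 and about an even chance at 400. Missing a tripling is more likely than not at 114 but unlikely at 400.
- **Miscarriage (10%).** A doubling is missed half the time at 114 and rarely at 400. The objection here is to the form of inference, not to rarity.

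These figures assume a Fisher test, equal groups, and 114 or 400 analysable participants in each. They do not show that the plan would declare safety whatever the truth.

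**What to change.** For all seven secondary endpoints, replace the aim of demonstrating no difference with: estimate the between-group difference with a 95% confidence interval. Specify:
- risk differences for the binary endpoints (2 to 6), with exact or score-based intervals where events are few;
- a mean difference for birth weight;
- a rate comparison for emergency and urgent-care visits. Survey question 39 records only yes or no, for headache admissions during pregnancy, so either the question must collect counts over the endpoint's full period or the measure must be matched to what is collected.

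Add one sentence to the Statistical Analysis Plan stating that a non-significant result on these endpoints will not be reported as evidence of no difference.

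The cost is endpoint and analysis wording, plus one survey item if counts are wanted. No more participants are needed. The plan already states a 95% precision for gestational age, so this extends its own approach. The sponsor gives up a claim that the data could not support.
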